8.0 Drugs and Devices

8.1 * DRUGS AND/OR BIOLOGICS: Are you **STUDYING** any drugs and/or biologics that are either approved or unapproved: **(REQUIRED)**

Yes No

Note: This question is frequently answered incorrectly. If any drugs or biologics, approved or unapproved, are being administered under this protocol, you should check 'Yes' unless you are *absolutely* sure that **NONE** of the drugs are part of the research protocol. Tip: Ask the PI or the sponsor if you are not sure how to answer this question.

8.3 * MEDICAL DEVICES: Are you **STUDYING** any medical devices, in vitro diagnostics, or assays that are either approved or unapproved: **(REQUIRED)**

Yes No

8.4 * NSR: Are you requesting a Non-Significant Risk (NSR) determination for an investigational device: **(REQUIRED)** **Note: an NSR determination is different from an Investigational Device Exemption (IDE). Check the Help link for more guidance on what types of devices can qualify for an NSR determination.**

Yes No

8.5 **LIST THE DEVICES:** List the medical devices or in vitro diagnostics to be studied or used. In the device details screen you will be asked questions such as:

- Whether the device is FDA approved or investigational
- Medicare device category
- If the device will be provided at no cost
- If an IDE is necessary, the IDE number, and who holds the IDE
- Risk category of the device
- FDA status of the device

Please see the [UCSF IRB website](#) for more details about the use of devices in research, including the [Investigator Checklist for Significant Risk, Non-Significant Risk, and/or IDE Exempt Device Studies](#)

Verification of IDE numbers: If the sponsor's protocol does not list the IDE number, you must submit documentation from the sponsor or FDA identifying the IDE number for this study. Attach this documentation in the Other Study Documents section of the Initial Review Submission Packet.

If you have any correspondence from the FDA or sponsor regarding this device, please attach it to the application.

View Details	Device Name	Is the Device FDA Approved	Is this a new device or a new use of an already approved device	IDE Number
	Activa PC Primary Cell Neurostimulator	Yes	Yes	G160233
Manufacturer/Supplier of Device		Medtronic		
Medicare Category		 A  B		
Where will the Devices Be Stored				
Will Devices be supplied at no Cost		No		
Is this a HUD (HDE)		No		

HDE Number	
Is the Device FDA Approved	Yes
Is this a new device or a new use of an already approved device	Yes
Is an IDE necessary	Yes
IDE Number	G160233
Who holds the IDE	PI holds the IDE
IDE Details	
In the opinion of the sponsor, select the level of risk associated with this device	Significant Risk

	Activa SC Single Cell Neurostimulator	Yes	Yes	G160233
--------------------------	---------------------------------------	-----	-----	---------

Manufacturer/Supplier of Device	Medtronic
Medicare Category	 A  B
Where will the Devices Be Stored	
Will Devices be supplied at no Cost	Yes
Is this a HUD (HDE)	No
HDE Number	
Is the Device FDA Approved	Yes
Is this a new device or a new use of an already approved device	Yes
Is an IDE necessary	Yes
IDE Number	G160233
Who holds the IDE	PI holds the IDE
IDE Details	
In the opinion of the sponsor, select the level of risk associated with this device	No Significant Risk

	Neurostimulator	Yes	Yes	G160233
--------------------------	-----------------	-----	-----	---------

Manufacturer/Supplier of Device	Medtronic
Medicare Category	 A  B
Where will the Devices Be Stored	
Will Devices be supplied at no Cost	No
Is this a HUD (HDE)	No
HDE Number	
Is the Device FDA Approved	Yes
Is this a new device or a new use of an already approved device	Yes
Is an IDE necessary	Yes
IDE Number	G160233
Who holds the IDE	PI holds the IDE
IDE Details	
In the opinion of the sponsor, select the level of risk associated with this device	Significant Risk

	DBS Lead	Yes	Yes	G160233
Manufacturer/Supplier of Device		Medtronic		
Medicare Category		 A  B		
Where will the Devices Be Stored				
Will Devices be supplied at no Cost		No		
Is this a HUD (HDE)		No		
HDE Number				
Is the Device FDA Approved		Yes		
Is this a new device or a new use of an already approved device		Yes		
Is an IDE necessary		Yes		
IDE Number		G160233		
Who holds the IDE		PI holds the IDE		
IDE Details				
In the opinion of the sponsor, select the level of risk associated with this device		Significant Risk		
	Activa SC Single Cell Neurostimulator	Yes	Yes	G160233
Manufacturer/Supplier of Device		Medtronic		
Medicare Category		 A  B		
Where will the Devices Be Stored				
Will Devices be supplied at no Cost		No		
Is this a HUD (HDE)		No		
HDE Number				
Is the Device FDA Approved		Yes		
Is this a new device or a new use of an already approved device		Yes		
Is an IDE necessary		Yes		
IDE Number		G160233		
Who holds the IDE		N/A		
IDE Details				
In the opinion of the sponsor, select the level of risk associated with this device		Significant Risk		
	Medtronic DBS extension	Yes	Yes	G160233
Manufacturer/Supplier of Device		Medtronic		
Medicare Category		 A  B		
Where will the Devices Be Stored				
Will Devices be supplied at no Cost		No		
Is this a HUD (HDE)		No		
HDE Number				
Is the Device FDA Approved		Yes		

Is this a new device or a new use of an already approved device	Yes
Is an IDE necessary	Yes
IDE Number	G160233
Who holds the IDE	PI holds the IDE
IDE Details	
In the opinion of the sponsor, select the level of risk associated with this device	Significant Risk

	DBS Extension	Yes	Yes	G160233
--------------------------	---------------	-----	-----	---------

Manufacturer/Supplier of Device	Medtronic
Medicare Category	 A  B
Where will the Devices Be Stored	
Will Devices be supplied at no Cost	No
Is this a HUD (HDE)	No
HDE Number	
Is the Device FDA Approved	Yes
Is this a new device or a new use of an already approved device	Yes
Is an IDE necessary	Yes
IDE Number	G160233
Who holds the IDE	PI holds the IDE
IDE Details	
In the opinion of the sponsor, select the level of risk associated with this device	Significant Risk

	Patient Programmer	Yes	Yes	G160233
--------------------------	--------------------	-----	-----	---------

Manufacturer/Supplier of Device	Medtronic
Medicare Category	 A  B
Where will the Devices Be Stored	
Will Devices be supplied at no Cost	No
Is this a HUD (HDE)	No
HDE Number	
Is the Device FDA Approved	Yes
Is this a new device or a new use of an already approved device	Yes
Is an IDE necessary	Yes
IDE Number	G160233
Who holds the IDE	PI holds the IDE
IDE Details	
In the opinion of the sponsor, select the level of risk associated with this device	Significant Risk

	Test Stimulator	Yes	Yes	G160233
--------------------------	-----------------	-----	-----	---------

Manufacturer/Supplier of Device	Medtronic
Medicare Category	 A  B
Where will the Devices Be Stored	
Will Devices be supplied at no Cost	No
Is this a HUD (HDE)	No
HDE Number	
Is the Device FDA Approved	Yes
Is this a new device or a new use of an already approved device	Yes
Is an IDE necessary	Yes
IDE Number	G160233
Who holds the IDE	PI holds the IDE
IDE Details	
In the opinion of the sponsor, select the level of risk associated with this device	Significant Risk

	N'Vision Clinician Programmer	Yes	Yes	G160233
--------------------------	-------------------------------	-----	-----	---------

Manufacturer/Supplier of Device	Medtronic
Medicare Category	 A  B
Where will the Devices Be Stored	
Will Devices be supplied at no Cost	No
Is this a HUD (HDE)	No
HDE Number	
Is the Device FDA Approved	Yes
Is this a new device or a new use of an already approved device	Yes
Is an IDE necessary	Yes
IDE Number	G160233
Who holds the IDE	PI holds the IDE
IDE Details	
In the opinion of the sponsor, select the level of risk associated with this device	Significant Risk

	N'Vision Software Application Card	Yes	Yes	G160233
--------------------------	------------------------------------	-----	-----	---------

Manufacturer/Supplier of Device	Medtronic
Medicare Category	 A  B
Where will the Devices Be Stored	
Will Devices be supplied at no Cost	No
Is this a HUD (HDE)	No
HDE Number	
Is the Device FDA Approved	Yes
Is this a new device or a new use of an already approved device	Yes

Is an IDE necessary	Yes
IDE Number	G160233
Who holds the IDE	PI holds the IDE
IDE Details	
In the opinion of the sponsor, select the level of risk associated with this device	Significant Risk

8.6 * Is this an expanded access or compassionate use protocol, meaning the primary purpose is to diagnose, monitor or treat a patient's condition, rather than the collection of safety and efficacy data of the experimental agent: (REQUIRED)

Yes No

9.0 Sample Size and Eligibility Criteria

9.1 ENROLLMENT TARGET: How many people will you enroll:

17

If there are multiple participant groups, indicate how many people will be in each group:

9.3 SAMPLE SIZE JUSTIFICATION: Explain how and why the number of people was chosen. For multi-site studies, this is referring to the number that will be enrolled across all sites:

This is a phase I pilot study of 15 participants to determine safety and tolerability as well as estimate effect size to inform planning of future larger trials that will test effectiveness. There is not sufficient data on the efficacy outcome measures to calculate sample size using statistical methods, thus the number of subjects was estimated based on a similar prospective study of DBS of globus pallidus (GPI) in adults with secondary dystonia in which a significant improvement was found using 13 subjects. We will screen up to 17 patients to achieve a total of 15 implanted.

9.4 * PARTICIPANT AGE RANGE: Eligible age ranges: (REQUIRED)

- 0-6 years
- 7-12 years
- 13-17 years
- 18-64 years
- 65+

9.5 * STUDY POPULATIONS: Data will be collected from or about the following types of people (check all that apply): (REQUIRED)

- Inpatients
- Outpatients
- Family members or caregivers
- Providers
- People who have a condition but who are not being seen as patients
- Healthy volunteers
- Students

- Staff of UCSF or affiliated institutions
- None of the above

9.6 * SPECIAL SUBJECT GROUPS: Check the populations that may be enrolled: (REQUIRED)

- Children / Minors
- Subjects unable to consent for themselves
- Subjects unable to consent for themselves (emergency setting)
- Subjects with diminished capacity to consent
- Subjects unable to read, speak or understand English
- Pregnant women
- Fetuses
- Neonates
- Prisoners
- Economically or educationally disadvantaged persons
- None of the above

If not already addressed in the Background and Significance questions in the Research Plan section or elsewhere, explain why it is appropriate to include the types of subjects checked above in this particular study:

The intervention is aimed at children and young adults because data from Deep Brain Stimulation (DBS) in other sites in the brain (globus pallidus) suggests that the earlier in the disease course DBS is performed the better the outcome. DBS of globus pallidus has been shown to be safe and effective in children as young as 7 years of age.

Describe the additional safeguards that have been included in the study to protect the rights and welfare of these subjects and minimize coercion or undue influence:

Here are some examples:

- evaluating capacity to consent for individuals who may be decisionally impaired (specify how)
- calibrating payment amounts to be non-coercive for the financially disadvantaged
- conducting more in-depth evaluations of subjects' understanding of the study and the voluntary nature of participation
- involving advocates in the consent process

More information and other safeguards are described here: **Vulnerable Subject Populations** and **Recruiting Staff and Students**.

Children and adolescents ages 7-17 will be asked to give verbal assent to the procedure. Subjects age 18 and over who are unable to give informed consent will have a surrogate give informed consent on their behalf.

9.7 INCLUSION CRITERIA: Briefly describe the population(s) that will be involved in this study. Include anyone that data will be collected from or about (e.g. patients, healthy controls, caregivers, providers, administrators, students, parents, family members, etc.):

1. Male or female between 7-25 years of age at Visit 2 (day of surgery).
2. Documentation of a secondary dystonia diagnosis as determined by a fellowship trained movement disorders specialist, including either abnormality on brain MRI or history of hypoxic-ischemic brain injury preceding onset of dystonia symptoms.
3. Symptoms present for at least 6 months.

4. Written informed consent and assent (when applicable) obtained from participant or participant's legal representative and ability for participant to comply with the requirements of the study.
5. Dystonia symptoms that are sufficiently severe, in spite of best medical therapy, to warrant surgical implantation of deep brain stimulators in the clinical opinion of the treating physician
6. Minimum score of Burke-Fahn-Marsden Rating Scale and/or Barry-Albright Dystonia Rating Scale of 6.
7. Stable doses of anti-dystonia medications (such as levodopa, baclofen, or diazepam) for at least 30 days prior to baseline assessment
8. If participant receives botulinum toxin injections, patient should be on a stable injection regimen (as defined as no changes in past 4 months)
9. Intact thalamic anatomy as determined by standard clinical MRI in the past 2 years.
10. Patient has been clinically determined to be a good candidate for deep brain stimulation.
11. A caregiver willing to administer rating scales related to the study

9.8 EXCLUSION CRITERIA: List any exclusion criteria (e.g. reasons why someone would not be included in the study):

- Pregnancy or breast feeding
- Major comorbidity increasing the risk of surgery (severe hypertension, severe diabetes, or need for chronic anticoagulation other than aspirin)
- Inability to comply with study protocols or follow-up visits
- Uncontrolled epilepsy (more than 1 seizure in the past 6 months)
- Has an active infection
- Requires diathermy, electroconvulsive therapy (ECT) or transcranial magnetic stimulation (TMS) to treat a chronic condition
- Has an active implanted neurostimulator, cardiac pacemaker, drug pumps, defibrillators, or metallic implant in head.
- Dystonia caused by known genetic mutation in any DYT genes
- Subjects with secondary dystonias caused by tardive dyskinesia associated with psychotropic medications or an ongoing inflammatory or infectious process.
- Subjects with cognitive impairment or dementia as defined by an estimated IQ of less than 70 on nonverbal IQ measures.
- Subjects with uncontrolled depression as diagnosed by board certified psychiatrist
- Subjects with uncontrolled co-existing medical conditions: e.g., uncontrolled systemic hypertension with values above 170/100; active heart disease needing immediate intervention; active respiratory disease needing immediate intervention; uncorrected coagulation abnormalities;
- Contraindication to undergo a brain MRI
- Subjects who are immunocompromised, are on anticoagulation therapy that would preclude their ability to undergo the implant procedure, and are allergic or have shown hypersensitivity to any materials of the neurostimulation system which come into contact in the body

9.9 * RESEARCH CONDUCTED ON PATIENT CARE WARDS: Do any study activities take place on patient care units at UCSF medical facilities: (REQUIRED)

Yes No

Attach a letter of acknowledgement for the study from the involved patient care manager. If you don't know who the patient care manager is, click [here](#) to send an email to the nursing group.

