11.0 Recruitment and Consent

11.1 * RECRUITMENT METHODS: What kinds of methods will be used to identify potential participants for recruitment (check all that apply): (REQUIRED)

- Medical records review
- Recruitment registry
- Re-contact of participants from the investigators' previous studies
- Referrals from colleagues (attach the 'Dear Colleague' letter or other recruitment materials you will provide to colleagues)
- Referrals from the community / word of mouth
- Advertisements (flyers, brochures, radio or t.v. ads, posting on clinical research sites or social media, presentation of the study at community events/media, etc.)
- Online recruiting tool such as TrialSpark
- CTSI Recruitment Services unit
- Other method (describe below)

11.2 * SEARCHING OF MEDICAL RECORDS: (REQUIRED)

Whose patients are they:

- Investigators' own patients or patients seen within the same practice
- Patients not under the care of the investigators

How and by whom will records be accessed and searched (check all that apply):

- Self-search in APeX or other medical records source
- Self-search using UCSF's Research Cohort Selection Tool
- CTSI Consultation Service Recruitment Services
- UCSF Academic Research Services (ARS)
- University of California Research Exchange (UC ReX)
- Other method (describe below)

11.3 DETERMINATION OF ELIGIBILITY: How, when, and by whom will eligibility for recruitment be determined:

Eligibility will be determined by the Investigator. After the Investigator determines that the patient and caregivers understand the risks and benefits, comprehend the consent, and have received satisfactory answers to all questions and signed the consent, the Investigator will determine eligibility based upon a complete history and physical, evaluation of screening assessment tools, and determination as to whether the patient meets all of the inclusion criteria and none of the exclusion criteria.

11.4 * INITIATION OF CONTACT: Who initiates contact (check all that apply): (REQUIRED)

- Investigators/study team
- UCSF recruitment unit (e.g. CTSI Consultation Services)
- Potential participant
- Other (explain below)

11.5 * HOW IS CONTACT INITIATED: (check all that apply): (REQUIRED)

- In person
- Phone
- Letter / email
- Website or app
- Other (explain below)

11.6 RECRUITMENT PLAN: Based on the checkboxes you chose above, please provide a narrative describing your recruitment plan. We want to know:

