- Infection: We anticipate that the infection rate in this patient population may be higher than the infection rate in Parkinson's disease, Essential Tremor, and primary dystonia. This is due to known higher infection rates in children compared with adults and the presence of a mixed movement disorder with a greater amount of hyperkinetic movements as compared with other movement disorders patients.
- Patient growth necessitating lead/extension length revision
- Patient brain/skull growth leading to lead migration: In cases where growth of the brain and/or skull is not complete at time of implant, the distance from the lead anchor point (burr hole) to the target site increases with time and growth of the individual. As a result, lead migration relative to the target site may occur.
- Children should be advised to avoid games, sports and other pastimes where a strain to the lead /connector assembly or a percussive injury to system components may be likely to occur (e.g., soccer, football/rugby).
- Intracranial hemorrhage

- Hemiplegia/Hemiparesis
- Paresis/asthenia
- Worsening of Motor Impairment
- Trouble swallowing
- Sensory Impairment (e.g., pain, paresthesia, sensory disturbance, hypesthesia, hearing/tinnitus)
- Headache
- Speech/Language disturbances (e.g., dysarthria, hypophonia)
- Subcutaneous Hemorrhage/Seroma
- Cerebral Spinal Fluid Abnormality
- Eye visual disturbances (e.g., diplopia, abnormal vision, visual field defect) and eye disorders (e.g., twitching)
- Cognitive disturbances (e.g., thinking abnormal, confusion, alteration of mentation) and Neuropsychological disturbances (e.g., depression, anxiety)

14.2 RISKS: Describe any anticipated risks and discomforts not listed above:

Potential Risks

General risks of DBS surgery (risks incurred by any patient having DBS implantation surgery, within or outside of this protocol)

General Anesthesia

There are always risks with general anesthesia. This may include a reaction to medications, myocardial infarction, or even death. There may be unknown risks.

Risks of the surgical procedure

Implanting the neurostimulator system carries the same risks associated with any other brain surgery. Risks may include:

- Paralysis, coma, and/or death
- Bleeding inside the brain (stroke)
- Leaking of fluid surrounding the brain

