- Air embolism (air bubble that enters an exposed blood vessel on the surface of the brain or in the skull bone, which can travel to the heart and possibly lung, a potentially life-threatening condition)
- Seizures
- Infection
- Allergic response to implanted materials
- Temporary or permanent neurological complications, including but not limited to decline in mental status, problems with speech, problems with movement or coordination
- Confusion or attention problems
- Pain at the surgery sites
- Headache

- Changes in hearing

Possible Device Complications

- There may be pain, lack of healing, or infection where the brain stimulation system parts are implanted. If this happens, further surgery or removal of part of the system may be necessary.
- The brain's stimulation system parts may wear through the skin which can cause an infection or scarring.
- The brain leads or lead/extension connectors may move. Further surgery to re-adjust the location may be needed.
- Components or parts of the brain stimulation system may suffer mechanical breakage resulting in loss of therapy. Further surgery to replace the system parts may be needed.
- The brain stimulation system could stop because of an electrical or software malfunction, which could require further surgery if noninvasive attempts to restore the software did not succeed.
- Battery in the pulse generator could be prematurely depleted. This would require further surgery. Pulse generator battery service life depends on individual use, but for most patients this should be > 2 years.
- There may be an allergic reaction to the brain stimulation system. The system materials coming in contact with the tissues include titanium, polyurethane, silicone, and nylon. The body could also reject the system (as a foreign body).
- There is the possibility of tissue damage resulting from the programming parameters or a malfunction of one of the parts of the brain stimulation system.

14.3

MINIMIZING RISKS: Describe the steps you have taken to minimize the risks/discomforts to subjects. Examples include:

- **designing the study to make use of procedures involving less risk when appropriate**
- **minimizing study procedures by taking advantage of clinical procedures conducted on the study participants**
- **mitigating risks by planning special monitoring or conducting supportive interventions for the study**
- **having a plan for evaluation and possible referral of subjects who report suicidal ideation**

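### The last exclusion in section 9.8 joins three conditions with 'and', so read literally no exclusion that names immunocompromise or device-material allergy removes a patient who has only those conditions

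*Combined protocol and SAP*

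**What the plan says.** The last exclusion in section 9.8 reads "Subjects who are immunocompromised, are on anticoagulation therapy that would preclude their ability to undergo the implant procedure, and are allergic or have shown hypersensitivity", and goes on to specify materials of the neurostimulation system that contact the body.

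Three other entries in the eligibility lists bear on the same ground:

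- An earlier bullet in 9.8 covers anticoagulation on its own: "Major comorbidity increasing the risk of surgery (severe hypertension, severe diabetes, or need for chronic anticoagulation other than aspirin". That list joins its items with 'or'.
- Another bullet in 9.8 is "Has an active infection".
- Inclusion 10 in section 9.7 is a general suitability test: "Patient has been clinically determined to be a good candidate for deep brain stimulation".

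Section 11.3 says how the lists are applied. The investigator takes a full history and examination, evaluates the screening tools, and makes a "determination as to whether the patient meets all of the inclusion criteria and none of the exclusion criteria".

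Section 14 lists the related hazards. Section 14.1 states "We anticipate that the infection rate in this patient population may be higher than the infection rate in Parkinson's disease", essential tremor and primary dystonia. Section 14.2 lists infection at the implant sites, possibly needing further surgery or removal of components. It also says "There may be an allergic reaction to the brain stimulation system" and that the body could reject the system.

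**The concern.** An exclusion list normally works item by item: any one listed condition keeps a patient out. The last bullet of 9.8 does not do that on its wording, because it strings three different conditions into one compound condition. They are unrelated to each other, and a patient with all three would be rare.

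Safety and tolerability are the first aim in section 7.3, the intervention is intracranial implantation, and enrolment starts at age 7. The protocol itself treats infection, allergic reaction and rejection as risks of the implant. The only written exclusion that names immunocompromise or material allergy should say clearly whether each condition alone keeps a patient out. As worded, two people checking the same patient against the same list could reach different answers, and a monitor or auditor could not say which was right.

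**Working it through.** No figure in the plan is involved, so there is nothing numerical to reproduce. The check has three steps.

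**1. Grammar of the bullet.** A single relative clause carries three predicates: immunocompromised (I), on anticoagulation that precludes the implant procedure (A), and allergic or hypersensitive to system materials (H). The joining word is 'and'. The only 'or' lies inside H. The literal rule is therefore I and A and H.

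**2. Enumeration.** There are 2 × 2 × 2 = 8 combinations. The fourth column assumes that the separate chronic-anticoagulation bullet catches every patient with A.

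| Combination | Bullet read literally | Bullet read as alternatives | Literal bullet plus chronic-anticoagulation bullet |
|---|---|---|---|
| none | no | no | no |
| I only | no | excluded | no |
| H only | no | excluded | no |
| I and H | no | excluded | no |
| A only | no | excluded | excluded |
| A and I | no | excluded | excluded |
| A and H | no | excluded | excluded |
| A, I and H | excluded | excluded | excluded |
| **Total excluded** | **1** | **7** | **4** |

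Under that assumption, 7 − 4 = 3 combinations are excluded on the alternative reading but not on the literal one: I only, H only, and I with H. If the separate bullet caught none of the A patients (for example because their treatment is short-term rather than chronic), the gap would be 7 − 1 = 6. So the gap lies between 3 and 6 combinations, and the three without A are open in either case. These are counts of logical combinations. They are not equally likely and are not counts of patients.

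**3. Search for other cover.**

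- The active-infection bullet concerns a current infection, which is a different condition from immunocompromise.
- The bullet on uncontrolled co-existing conditions is an open list of examples. It names neither condition, although it might be stretched to reach some immunocompromised patients.
- Section 14.3, on minimising surgical risk, restates the comorbidity exclusion and names neither condition.
- Inclusion 10, and less directly inclusion 5 (severity sufficient to warrant surgery in the treating physician's opinion), leave room for judgement but name neither condition.

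The last bullet of 9.8 is therefore the only eligibility criterion that names immunocompromise or material allergy.

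**Anticoagulation.** The list applies two tests: a chronic need other than aspirin, and therapy that precludes the procedure. They can differ for the same patient. A chronic need that can be managed around surgery meets the first and not the second; short-term therapy that blocks surgery meets the second and not the first.

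**The case against.** The strongest reply is that nobody would apply the bullet literally. Its middle item already describes patients who cannot undergo the procedure, so requiring them also to be immunocompromised and allergic defeats the purpose. The sentence can be read as a list of kinds of excluded subject. At a single center where the investigator decides eligibility, nothing in the documents suggests that the all-three reading would be used. This stands as an account of what was probably meant. It does not make the bullet say it.

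A reader might infer that an immunocompromised or allergic child is thereby cleared for implantation. The documents do not support that. Section 11.3 requires all inclusion criteria to be met, and inclusion 10 lets the clinician decline such a patient. What is missing is an exclusion that clearly applies to the condition by name.

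A reader might also infer that the protocol ranks infection and allergy as its leading harms, or that it links its expected infection rate to immune status. It does neither. The study stopping criteria in 15.2 name hemorrhage, subdural hematoma, seizures, neurological worsening and death. Section 14.1 attributes the higher infection rate to known higher rates in children and to more hyperkinetic movement.

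Finally, one event among 15 implanted subjects is 1/15 = 6.7 percentage points, but that is the weight of any single event in this trial and does not measure this defect.

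On anticoagulation, if the bullet is read as alternatives the overlap is harmless, because meeting either test excludes. That is fair, but it depends on the wording being settled first.

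**Conclusion.** The point holds in a limited form. Read literally, the last exclusion in 9.8 applies only to a patient with all three conditions. A patient with immunocompromise, device-material allergy or both, but without precluding anticoagulation, is removed by no exclusion that names the condition and depends on general judgement under inclusion 10.

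This is a defect in an operative eligibility rule, probably a drafting slip. It has no effect on the sample size or the analysis. Its practical size cannot be given: the documents state neither how common these conditions are among candidates nor how the site reads the bullet. The conclusion rests on the literal wording and on the absence of the two conditions from every other criterion in 9.7 and 9.8. It does not rest on any assumption about event rates.

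**What to change.** Rewrite the last bullet of 9.8 as three separate exclusions, or replace the joining 'and' with 'or', so that each condition alone excludes. If the conjunction is intended, the sponsor should say so and explain it.

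Reconcile the bullet's anticoagulation wording with the separate chronic-anticoagulation exclusion, so that a reader can tell how the two tests relate. Which threshold applies is a clinical decision for the sponsor.

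The cost is a one-line amendment to the eligibility section, plus matching wording in any eligibility checklist. No change to the sample size, visits or analysis is needed.
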